cfDNA	circulating cell-free DNA
CI	confidence interval
CL	Clearance
C _{max}	maximum concentration
CNS	central nervous system
CR	complete response
CRO	contract research organization
CRR	complete response rate
CSR	clinical study report
CT	computed tomography
CTCAE	Common Terminology Criteria for Adverse Events
DLBCL	diffuse large B-cell lymphoma
DNA	deoxyribonucleic acid
DOR	duration of response
ECG	electrocardiogram
ECOG	Eastern Cooperative Oncology Group
eCRF	electronic case report form
EDC	electronic data capture

Abbreviation	Definition
EOT	end of treatment
EQ-5D-5L	EuroQol–5 Dimensions–5 Levels
EU	European Union
FACT-Lym	Functional Assessment of Cancer Therapy - Lymphoma
FDA	Food and Drug Administration
FFPE	formalin-fixed paraffin-embedded
GCP	Good Clinical Practice
gDNA	genomic DNA
GGT	gamma glutamyl transferase
H0	null hypothesis
H1	first hypothesis
H2	second hypothesis
Ha	alternate hypothesis
HBV	hepatitis B virus
β-HCG	beta human chorionic gonadotropin
HCV	hepatitis C virus
HD-ASCT	high-dose chemotherapy and autologous stem cell transplant
HIV	human immunodeficiency virus
hr	hour
HRQoL	health-related quality of life
IB	Investigator’s Brochure
ICF	informed consent form
ICH	International Council for Harmonisation
IEC	independent ethics committee
INR	international normalized ratio
IRB	institutional review board
IRC	independent review committee
IV	intravenous
MedDRA	Medical Dictionary for Regulatory Activities
mmHg	millimeters of mercury
MRI	magnetic resonance imaging
MSD-ECL	Meso-Scale Discovery Electrochemiluminescence
MTD	maximum tolerated dose
NHL	non-Hodgkin lymphoma
ORR	overall response rate
OS	overall survival
PBD	pyrrolbenzodiazepine
PD	progressive disease
PET	positron emission tomography
PFS	progression-free survival
PK	Pharmacokinetic(s)
PO	per os
pp	predicted probability
PR	partial response
PTT	partial thromboplastin time

Abbreviation	Definition
QT	measure between Q wave and T wave in the electrocardiogram
QTcF	Fridericia correction of the QT measure
Q3W	every 3 weeks
RBC	red blood cell
RFS	relapse-free survival
RR	respiratory rate
SAE	serious adverse event
SAP	statistical analysis plan
SCT	stem cell transplantation
SD	stable disease
SOC	standard of care
SoE	schedule of events
SUSAR	Suspected Unexpected Serious Adverse Reactions
TEAE	treatment-emergent adverse event
TLS	tumor lysis syndrome
T _{max}	time to maximum concentration
μL	microliter
ULN	upper limit of normal
US	United States
Val	valine
VAS	visual analog scale
WBC	white blood cell
WHO	World Health Organization
wk	week
WOCBP	woman of childbearing potential

Protocol Synopsis

Protocol Number:	ADCT-402-201
Title:	A Phase 2 Open-Label Single-Arm Study to Evaluate the Efficacy and Safety of Loncastuximab Tesirine in Patients with Relapsed or Refractory Diffuse Large B-Cell Lymphoma (DLBCL)
Sponsor:	ADC Therapeutics SA
Study Phase:	Phase 2
Indication:	Diffuse Large B-Cell Lymphoma (DLBCL)
Rationale:	
Non-Hodgkin lymphoma (NHL) is the seventh most common type of cancer in the US, and account for an estimated 4.3% of new cancer cases in 2017. DLBCL accounts for nearly one-third (32.5%) of NHL. Chemo-immunotherapy, with or without radiotherapy, is the most common initial treatment for DLBCL. Response to initial treatment is high; however, a significant proportion of patients relapse. The current standard of care for relapsed DLBCL is additional chemotherapy, which can be followed by stem cell transplantation (SCT). The poor prognosis for relapsed patients, especially those with chemo-refractory disease with a short interval between remission and relapse, or those who relapse after high-dose therapy and SCT, highlights the unmet needs for patients with relapsed or refractory DLBCL.
 
Human CD19 antigen is a 95 kd transmembrane glycoprotein belonging to the immunoglobulin superfamily. In normal human tissue, expression of CD19 continues through pre-B and mature B-cell differentiation until it is finally down-regulated during terminal differentiation into plasma cells; however, expression of CD19 is maintained in hematologic B-cell malignancies, including DLBCL.
 
Loncastuximab tesirine (ADCT-402) is an antibody drug conjugate (ADC) that has been designed to target and kill CD19-expressing malignant B-cells. Preliminary data from a Phase 1 study of loncastuximab tesirine in relapsed or refractory B-cell NHL shows significant activity in patients with DLBCL.

Objectives:	
Primary Objective
 
• Evaluate the efficacy of single agent loncastuximab tesirine in patients with relapsed or refractory DLBCL 
Secondary Objectives
 
• Characterize the safety profile of loncastuximab tesirine• Characterize the pharmacokinetic (PK) profile of loncastuximab tesirine• Evaluate the immunogenicity of loncastuximab tesirine• Evaluate the impact of loncastuximab tesirine treatment on health-related quality of life (HRQoL) 
[REDACTED]
 
[REDACTED]
 
[REDACTED]

Endpoints:

Primary Endpoint

Overall response rate (ORR) according to the 2014 Lugano classification as determined by central review in all treated patients; ORR is defined as the proportion of patients with a best overall response (BOR) of complete response (CR) or partial response (PR)

Secondary Endpoints

- Duration of response (DOR) defined as the time from the first documentation of tumor response to disease progression or death
- CR rate defined as the percentage of treated patients with a BOR of CR
- Relapse-free survival (RFS) defined as the time from the documentation of CR to disease progression or death
- Progression-free survival (PFS) defined as the time between start of treatment and the first documentation of recurrence, progression, or death
- Overall survival (OS) defined as the time between the start of treatment and death from any cause
- Frequency and severity of adverse events (AEs) and serious adverse events (SAEs)
- Changes from baseline of safety laboratory values, vital signs, Eastern Cooperative Oncology Group (ECOG) performance status, and 12-lead electrocardiograms (ECGs)
- Concentrations and PK parameters of loncastuximab tesirine total antibody, pyrrolobenzodiazepine (PBD)-conjugated antibody, and unconjugated warhead SG3199
- Anti-drug antibody (ADA) titers and, if applicable, neutralizing activity to loncastuximab tesirine after treatment with loncastuximab tesirine
- Change from baseline in HRQoL as measured by EuroQoL-5 Dimensions-5 Levels (EQ-5D-5L) and Functional Assessment of Cancer Therapy - Lymphoma (FACT-Lym)

[REDACTED]

[REDACTED]

[REDACTED]

Study Design:

This is a Phase 2, multi-center, open-label, single-arm study. The study will enroll approximately 140 patients.

A 2-stage design will be used, with an interim analysis for futility on the first 52 patients. If ≥ 10 patients respond (CR+PR), the study will proceed to complete full enrollment. Enrollment will continue during the interim analysis; however, further enrollment will be halted if futility is confirmed.

Patient Selection:

Inclusion Criteria:

1. Male or female patient aged 18 years or older
2. Pathologic diagnosis of DLBCL, as defined by the 2016 WHO classification, to include: DLBCL not otherwise specified; primary mediastinal large B-cell lymphoma; and high-grade B-cell lymphoma, with *MYC* and *BCL2* and/or *BCL6* rearrangements
3. Relapsed or refractory disease following two or more multi-agent systemic treatment regimens
4. Patients who have received previous CD19-directed therapy must have a biopsy that shows CD19 protein expression after completion of the CD19-directed therapy
5. Measurable disease as defined by the 2014 Lugano Classification
6. Availability of formalin-fixed paraffin-embedded (FFPE) tumor tissue block (or minimum 10 freshly cut unstained slides if block is not available)

Note: Any biopsy since initial diagnosis is acceptable, but if several samples are available, the most recent sample is preferred.

7. ECOG performance status 0-2
8. Adequate organ function as defined by screening laboratory values within the following parameters:
 - a. Absolute neutrophil count (ANC) $\geq 1.0 \times 10^3/\mu\text{L}$ (off growth factors at least 72 hours)
 - b. Platelet count $\geq 75 \times 10^3/\mu\text{L}$ without transfusion in the prior 7 days
 - c. Alanine aminotransferase (ALT), aspartate aminotransferase (AST), and gamma glutamyl transferase (GGT) $\leq 2.5 \times$ the upper limit of normal (ULN)
 - d. Total bilirubin $\leq 1.5 \times$ ULN (patients with known Gilbert's syndrome may have a total bilirubin up to $\leq 3 \times$ ULN)
 - e. Blood creatinine $\leq 1.5 \times$ ULN or calculated creatinine clearance ≥ 60 mL/min by the Cockcroft and Gault equation

Note: A laboratory assessment may be repeated a maximum of two times during the Screening period to confirm eligibility.

9. Negative beta-human chorionic gonadotropin (β -HCG) pregnancy test within 7 days prior to start of study drug (C1D1) for women of childbearing potential
10. Women of childbearing potential must agree to use a highly effective method of contraception from the time of giving informed consent until at least 16 weeks after the last dose of loncastuximab tesirine. Men with female partners who are of childbearing potential must agree that they will use a highly effective method of contraception from the time of giving informed consent until at least 16 weeks after the patient receives his last dose of loncastuximab tesirine

Exclusion Criteria:

1. Previous treatment with loncastuximab tesirine
2. Known history of hypersensitivity to or positive serum human ADA to a CD19 antibody
3. Pathologic diagnosis of Burkitt lymphoma
4. Bulky disease, defined as any tumor ≥ 10 cm in longest dimension
5. Active second primary malignancy other than non-melanoma skin cancers, non-metastatic prostate cancer, in situ cervical cancer, ductal or lobular carcinoma in situ of the breast, or other malignancy that the Sponsor's medical monitor and Investigator agree and document should not be exclusionary
6. Autologous stem cell transplant within 30 days prior to start of study drug (C1D1)
7. Allogeneic stem cell transplant within 60 days prior to start of study drug (C1D1)
8. Active graft-versus-host disease
9. Post-transplant lymphoproliferative disorders
10. Active autoimmune disease, including motor neuropathy considered of autoimmune origin and other central nervous system (CNS) autoimmune disease
11. Known seropositive and requiring anti-viral therapy for human immunodeficiency virus (HIV), hepatitis B virus (HBV), or hepatitis C virus (HCV). Note: Testing is not mandatory to be eligible
12. History of Stevens-Johnson syndrome or toxic epidermal necrolysis
13. Lymphoma with active CNS involvement at the time of screening, including leptomeningeal disease
14. Clinically significant third space fluid accumulation (i.e., ascites requiring drainage or pleural effusion that is either requiring drainage or associated with shortness of breath)
15. Breastfeeding or pregnant
16. Significant medical comorbidities, including but not limited to, uncontrolled hypertension (blood pressure [BP] $\geq 160/100$ mmHg repeatedly), unstable angina, congestive heart failure (greater than New York Heart Association class II), electrocardiographic evidence of acute ischemia, coronary angioplasty or myocardial infarction within 6 months prior to screening, uncontrolled atrial or ventricular cardiac arrhythmia, poorly controlled diabetes, or severe chronic pulmonary disease
17. Major surgery, radiotherapy, chemotherapy, or other anti-neoplastic therapy within 14 days prior to start of study drug (C1D1), except shorter if approved by the Sponsor
18. Use of any other experimental medication within 14 days prior to start of study drug (C1D1)
19. Planned live vaccine administration after starting study drug (C1D1)
20. Failure to recover to Grade ≤ 1 (Common Terminology Criteria for Adverse Events [CTCAE] version 4.0) from acute non-hematologic toxicity (Grade ≤ 2 neuropathy or alopecia) due to previous therapy prior to screening

	
21. Congenital long QT syndrome or a corrected QTcF interval of >480 ms at screening (unless secondary to pacemaker or bundle branch block)
 
22. Any other significant medical illness, abnormality, or condition that would, in the Investigator's judgment, make the patient inappropriate for study participation or put the patient at risk

Estimated Duration of Patient Participation and Study Duration:
	
The duration of the study participation for each patient is defined as the time from the date of signed written informed consent to the completion of the follow-up period, withdrawal of consent, loss to follow-up, or death, whichever occurs first.
 
The study will include a Screening Period (of up to 28 days), a Treatment Period (cycles of 3 weeks), and a Follow-up Period (approximately every 12 week visits for up to 3 years after treatment discontinuation).
 
Patients may continue treatment until disease progression, unacceptable toxicity, or other discontinuation criteria, whichever occurs first.
 
The end of study occurs at the last visit or last scheduled procedure for the last patient, unless the study is terminated earlier by Sponsor.


Efficacy Assessments:
	
• Disease assessments: Positron emission tomography - computed tomography (PET-CT) 
Note: If disease is not PET-avid at baseline, CT or magnetic resonance imaging (MRI) may be used for follow-up disease assessments. The assessment method determined to identify sites of disease at baseline should be used for all subsequent assessments.

Safety Assessments:
	
• Physical examination• ECOG Performance status• Height and weight• Vital signs• Safety laboratories (hematology, chemistry, coagulation, urinalysis)• Pregnancy test, if applicable• 12 Lead-ECG (triplicate)• AEs/SAEs, graded according to CTCAE version 4.0.

Other Assessments:
	
• Blood sampling for PK, ADA, [REDACTED]• [REDACTED]• [REDACTED]• HRQoL: EQ-5D-5L and FACT-Lym

Study Drug, Dosage, and Mode of Administration:
	
Loncastuximab tesirine will be administered as an intravenous (IV) infusion over 30 minutes on Day 1 of each cycle. Patients will receive 150 µg/kg every 3 weeks (Q3W) for 2 cycles, then 75 µg/kg Q3W for subsequent cycles.
 
Patients with a body mass index (BMI) ≥ 35 kg/m² will have their dose calculated based on an adjusted body weight.

Sample Size:
	
Approximately 140 patients.

**Statistical
Considerations:**

Study Hypotheses:

H1: ORR based on central review for patients treated with loncastuximab tesirine is significantly greater than 20% (i.e., H0: $p \leq 0.2$ vs. Ha: $p > 0.2$).

Sample Size Justification:

Using nQuery exact test for single proportion, a sample size of 140 patients has >99% power to achieve a 1-sided significance level of 0.025 (2-sided significance level of 0.05). This sample size will provide adequate precision for observed ORR in the expected range and a robust population for safety evaluation.

Statistical Analysis:

ORR and CR rate with 95% CI from all treated patients will be presented. DOR, PFS, RFS, and OS will be analyzed by Kaplan-Meier approach. Safety analyses will be presented descriptively.

Schedule of Events

Table 1. Schedule of Events

	Protocol Section	Screening	Treatment Period				EOT	Follow-up Period (up to 3 years from EOT) Every 12 weeks
			Cycle 1 and Cycle 2 (C1 and C2)		C3 and beyond			
(1 Cycle = 3 weeks)			Cycle 1	Cycle 2				
Day (D)		-28 to -1	1	8	15	1		
Informed consent	11.3	X						
Eligibility criteria	5	X						
Demography	9.5	X						
Medical/Cancer history	9.5	X						
██████████	██████████	██████████						
Physical examination	8.3.1	X	X			X	X	
ECOG performance status	8.3.2	X	X			X	X	
Height	8.3.3	X						
Weight	8.3.3	X	X	X	X	X	X	
Vital signs (BP, HR, RR, Temp)	8.3.4	X	X	X	X	X	X	
Disease assessment ²	8.1	X	6 weeks and 12 weeks after C1D1, then every 9 weeks				X ²	Every 12 weeks until 1 year from EOT, then every 6 months until disease progression ³
Hematology and Chemistry	8.3.5	X	X ⁴	X	X	X ⁴	X	
Coagulation and Urinalysis	8.3.5	X						
Pregnancy test, if applicable	8.3.6	X	X ⁵			X	X	
12-lead ECG	8.3.7 Table 4	X	X (pre-infusion, EOI, and 4 h post-infusion)	X	X	Every other cycle (C3, pre-infusion and EOI; C5 and beyond, pre-infusion only)	X	
Premedication	6.6.1		D-1 to D2			D-1 to D2		
Loncastuximab tesirine administration	6.3		X			X		

	Protocol Section	Screening	Treatment Period				EOT	Follow-up Period (up to 3 years from EOT) Every 12 weeks
			Cycle 1 and Cycle 2 (C1 and C2)		C3 and beyond			
(1 Cycle = 3 weeks)			1	8	15	1		
Day (D)		-28 to -1	1	8	15	1		
PK sample	8.4.1 Table 5		X (pre-infusion, EOI, and 4 h post-infusion)	X	X	Every other cycle (C3, pre-infusion and EOI; C5 and beyond, pre-infusion only)	X	
ADA sample	8.4.2 Table 5		X (pre-infusion)		X ⁶	Every other cycle (C3 and beyond, pre-infusion only)	X ⁷	
gDNA and cfDNA samples	8.4.3		X				X	
HRQoL	8.5		X			X	X	
Concomitant medications	6.7	From ICF signature date or D-14 whichever is earlier, until at least 30 days after last dose of study drug						
Adverse events	8.2	CTCAE, Version 4.0 AE/SAEs from ICF signature date until at least 30 days after last dose of study drug; thereafter related SAEs only						
1 st New anticancer treatment							X	
Survival							X	

Abbreviations: ADA, anti-drug antibody; AE, adverse event; BP, blood pressure; cfDNA, circulating cell-free DNA; CTCAE, Common Terminology Criteria for Adverse Events; ECG, electrocardiogram; ECOG, Eastern Cooperative Oncology Group; EOI, end of infusion; EOT, end of treatment; gDNA, genomic DNA; HR, heart rate; HRQoL, health-related quality of life; ICF, informed consent form; PET-CT, Positron emission tomography - computed tomography; PK, pharmacokinetics; RR, respiratory rate; SAE, serious adverse event; Temp, temperature.

¹ Tumor tissue should be submitted once all other eligibility criteria have been met.

² Screening imaging (PET-CT) must be performed within 4 weeks prior to C1D1 and the same assessment method should be used throughout the study. Week 6 imaging should be performed within 5 days prior to C3D1 and Week 12 imaging should be performed within 5 days prior to C5D1. All other imaging for disease assessment for patients on study drug should be performed within ± 2 weeks of the scheduled timepoint. Disease assessments should be performed at the timepoints specified even if study drug dosing is delayed. If a scan has been performed within 8 weeks of EOT, it does not need to be repeated at EOT.

³ Disease assessments to be performed in patients having discontinued study drug for reasons other than disease progression.

⁴ ≤3 days prior to administration of study treatment, unless more frequent testing is clinically indicated.

⁵ Not needed if screening assessment was performed within 7 days prior to C1D1.

⁶ Cycle 1 only

⁷ Patients who test positive for ADAs will be requested to supply additional ADA samples as per [Section 8.4.2](#).

Visit Scheduling Windows:

- Treatment Period: visit day ± 2 days (excluding C1D1 which is the reference day)
- EOT: as soon as possible after decision to discontinue the study drug, preferably within 30 days after last dose of study drug, and before initiation of any new anticancer treatment
- Follow-up Period: visit day ± 14 days

1 Introduction and Background

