9.7.3 Additional Safety Assessments

The results of scheduled assessments of vital signs, physical examinations, ECOG performance status, and 12-lead ECGs will be summarized. All data will be reported according to the nominal visit date for which it was recorded (i.e., no visit windows will be applied). Unscheduled data will be included in “worst case” summaries, which will capture a worst case across all scheduled and unscheduled visits after the first dose of study drug. All data will be listed. Further details will be provided in the SAP.

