4.8.5 ECOG Performance Status

Descriptive statistics (mean, standard deviation, median and range) will be calculated for the raw data and for their changes from baseline at each scheduled assessment.

Summary analyses will include data up to the start of subsequent anticancer therapy/procedure.

ECOG performance score data will be listed.

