7.1.2 Unscheduled visits

Unscheduled visit measurements of laboratory data, vital signs, and ECG will be used for computation of baseline and worst values and/or grades. Re-windowing for unscheduled visits will not be performed

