14.3.8 ECOG DATA TABLE

14.3.8.1 Summary of ECOG Performance Score by Visits (All-Treated Population)

14.3.9 PRO DATA TABLE

14.3.9.1.1 Summary of EQ-5D-5L VAS Score by Visits (PRO Population)

14.3.9.1.2 Frequency Distribution of the Individual Dimension Response from EQ-5D-5L Descriptive System by Visits (PRO Population)

14.3.9.1.3 Summary of Patients Classified as Improvement/Deterioration Based on Minimally Clinically Important Difference for EQ-5D-5L VAS Score (PRO Population)

14.3.9.1.4 Completion Rate for EQ-5D-5L Descriptive System and VAS Score by Visit (PRO Population)

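### The SAP gives ECOG performance status only by-visit continuous statistics and a listing, and omits, without declaring it, the worst-case summary stated in protocol 9.7.3

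*Protocol*

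**What the plan says.** The Protocol Synopsis names among the secondary endpoints "Changes from baseline of safety laboratory values, vital signs, Eastern Cooperative Oncology Group (ECOG) performance status, and 12-lead electrocardiograms (ECGs". Protocol 9.7.3 sets the scope of the analysis: "The results of scheduled assessments of vital signs, physical examinations, ECOG performance status, and 12-lead ECGs will be summarized". The same paragraph puts unscheduled data into worst-case summaries, "which will capture a worst case across all scheduled and unscheduled visits after the first dose of study drug", and leaves further detail to the SAP.

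For ECOG, SAP 4.8.5 provides: "Descriptive statistics (mean, standard deviation, median and range) will be calculated for the raw data and for their changes from baseline at each scheduled assessment". It stops the summaries when new anticancer therapy begins and adds that "ECOG performance score data will be listed". It plans no counts per grade, no shift table and no worst post-baseline grade.

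SAP 7.1.2 states the rule for unscheduled data: "Unscheduled visit measurements of laboratory data, vital signs, and ECG will be used for computation of baseline and worst values and/or grades". ECOG is not named, and the section rules out reassigning unscheduled visits to visit windows. The only ECOG table in SAP Appendix 2 is "14.3.8.1 Summary of ECOG Performance Score by Visits (All-Treated Population". SAP 3.3, which is reserved for departures from the protocol's statistical section, reads NA.

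**The concern.** ECOG is an ordinal grade from 0 to 5 (Protocol Appendix 1). The natural safety questions are how many patients got worse, and how far each patient fell at worst. By-visit continuous statistics answer neither, because one patient's improvement offsets another's decline and because visits are never linked within a patient. The worst-case summary in protocol 9.7.3 supplies that link, and the SAP leaves it out for ECOG without saying so. At stake is whether the clinical study report can state the frequency of functional decline on treatment, and whether grades recorded between scheduled visits enter any summary.

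**Working it through.** **Comparison of the documents.** There is no stated figure to reproduce. The check is how each safety variable with a worst-case commitment in the protocol is carried into the SAP.

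| Variable | Protocol worst case | SAP analysis section | Named in SAP 7.1.2 | Tables in SAP Appendix 2 |
|---|---|---|---|---|
| Laboratory | 9.7.2, yes | 4.8.2: by visit, shifts, worst case | yes | by visit, shift, maximum grade |
| ECG | 9.7.3, yes | 4.8.3: by visit, plus QTc categories at any post-baseline time | yes | by visit, QTc abnormality, QTc shift |
| Vital signs | 9.7.3, yes | 4.8.4: by visit | yes | by visit and time point |
| ECOG | 9.7.3, yes | 4.8.5: by visit | no | by visit |

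ECOG is the only row with no provision for a worst value in either its own section or 7.1.2. It also departs from the SAP's own practice. SAP section 4 makes counts and percentages the default for categorical data, and SAP 4.10.1 applies them to the EQ-5D-5L dimensions, which are five-level ordinal items.

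**What the planned statistics can show.** The distributions below are assumed; only N = 140 comes from the protocol (4.1).

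*Two-grade declines.* Let k patients worsen by 2 grades, 2k improve by 1, and the rest not change.
- Mean change = (2k - 2k)/140 = 0.
- SD = sqrt((4k + 2k)/139) = sqrt(6k/139).
- Median = 0 for each k below, since at most 56 of 140 are below zero and at most 28 above it.

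| k | Share worse by 2 | Mean | Median | Range | SD |
|---|---|---|---|---|---|
| 1 | 0.7% | 0 | 0 | -1 to 2 | 0.21 |
| 14 | 10% | 0 | 0 | -1 to 2 | 0.78 |
| 28 | 20% | 0 | 0 | -1 to 2 | 1.10 |

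*One-grade declines.* If m patients worsen by 1 and m improve by 1, the mean and median are 0, the range is -1 to 1, and SD = sqrt(2m/139). For m = 14, 28 and 42 (10%, 20%, 30%) the SD is 0.45, 0.63 and 0.78. Only the SD moves within each set, and it cannot be read back to a frequency: 0.78 arises from 10% worsening by two grades and from 30% worsening by one, although the range separates those two cases.

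*Linking visits.* Suppose 10% of patients are one grade worse at each of six visits and nobody improves. The mean change is 0.10 every time. The share ever worse is 10% if they are always the same patients, 1 - 0.9^6 = 46.9% if visits are independent, and up to 6 x 10% = 60% if they are different patients each time. Only a per-patient worst grade tells these apart.

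**Unscheduled values.** SAP 4.8.5 is limited to scheduled assessments, 7.1.2 does not bring ECOG in, and there is no re-windowing. An unscheduled post-dose ECOG grade therefore appears only in the listing.

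**The case against.** The strongest reply is that the gap is narrow, and several parts of that reply stand.

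- A reader might infer that ECOG is analysed only as means and that deterioration is averaged away. The documents do not support that. SD, median and range are planned and individual data are listed. The range shows the largest decline at each scheduled visit; what is missing is its frequency, each patient's worst grade and unscheduled values.
- A reader might infer that vital signs are dropped in the same way. They are not: SAP 7.1.2 names them for worst values, and only a line in 4.8.4 to report those values is lacking.
- A reader might infer that patients who stop treatment drop out of view, because each cycle row contains only those still treated. The Schedule of Events also has ECOG at end of treatment, and per-grade counts by visit would have the same denominators.
- Protocol 8.3.2 ties ECOG to the Schedule of Events, and nothing shows how many unscheduled grades will exist. That loss is possible but not quantified.
- Protocol 9.7.3 requires a worst-case summary. It does not prescribe a shift table or per-grade counts, and it does not rule out the planned means.
- Adverse events by maximum grade (SAP 4.8.1.1) and proportions improved or deteriorated on EQ-VAS and FACT-Lym (SAP 4.10) give related information, though none of it is a worst ECOG grade.

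Two further defences do not succeed. The Appendix 2 table list may change without a SAP update, but the gap is in 4.8.5 and 7.1.2 themselves. Protocol 9.7.3 still applies in principle, but it defers detail to a SAP that gives none here, and a listing is not a summary.

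**Conclusion.** The point holds as a mismatch between protocol and SAP on one secondary safety endpoint. Protocol 9.7.3 states a worst-case ECOG summary; SAP 4.8.5 and 7.1.2 do not provide it, and SAP 3.3 does not declare the omission. The planned tables show the centre, spread and extremes of ECOG change at each scheduled visit, but not how many patients deteriorated or any decline seen at an unscheduled visit.

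The size is modest. The endpoint is descriptive, SAP 4.8 plans no systematic testing of safety variables, and the primary response analysis is unaffected. The numerical examples rest on assumed distributions and show what the planned statistics cannot distinguish; they do not predict what this trial will find. The conclusion assumes that the protocol text supplied is the version on which the SAP was built.

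**What to change.** 1. **SAP 4.8.5:** add n (%) per ECOG grade at each scheduled visit. Add a shift table from baseline to worst post-baseline grade over all scheduled and unscheduled assessments until new anticancer therapy starts. Give n (%) whose worst grade exceeds baseline, among patients with a baseline and at least one post-baseline grade. The mean, SD, median and range may remain.
2. **SAP 7.1.2:** add ECOG to the variables whose unscheduled values count towards baseline and worst values.
3. **SAP 4.8.4:** add a line to report the worst vital-signs values that 7.1.2 already provides for.
4. **Appendix 2:** list the new tables.

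If the sponsor prefers not to produce a worst-case ECOG summary, SAP 3.3 should declare and justify the departure from protocol 9.7.3.

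The cost is SAP wording and one or two short descriptive tables from data already collected. No sample size, error rate or primary analysis changes.
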